		
Interim Analysis
 
Updated intercurrent event wording for estimands
 
Updated well to sick analysis
 
Clarified definition of return to well state
	
evaluate the study primary and secondary objectives, and the algorithm development analyses detailed in appendix SAP based on Cohort 1 data (consisting of approximately 9,100 participants who have been enrolled by 15 Feb 2022 prior to protocol amendment #2).
 
Section 2.1 and throughout the SAP: the intercurrent event wording for estimands in this study was clarified. There are no particular intercurrent events considered.
 
Section 5.2.2.3: The baseline for well to sick analysis was clarified. To categorize participants during well to sick and facilitate model convergence, the main well to sick analysis was updated to include: 1) a summary was added with respect to those who lack data during the period, non-responders for the endpoint, and responders (for which the days to maximal response and the growth rate will be summarized); 2) a linear mixed effect model was added to evaluate the overall trend for the endpoint; and 3) for endpoints that are statistically significant from 2), the nonlinear sigmoid model was modified to primarily use the logit transformed linear mixed effect model to estimate growth during the period.
 
Section 5.2.2.5: a clarification for return to well state was added, using the participants' initial 3-day symptoms.

Table 1. Summary of Changes

Version/ Date	Associated Protocol Amendment	Rationale	Specific Changes

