5.2.2.2. Definition of Recovery Phase

To define the recovery phase for each participant who has new or increased symptoms (as defined in [Section 5.2.2.1](#)), firstly the maximal total symptom score on or after the first occurrence of new or increased symptoms, as well as the first day on which this maximal total symptom score is reached (defined as the Maximal Score Day), are identified.

Then the beginning of recovery is defined as the first day after the Maximal Score Day when the total symptom score is decreased from the previous day with available symptom data, followed by two more days of non-increasing total symptom scores.

When no beginning of recovery is observed, all days up to the final study day of the participant are considered as before recovery.

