In addition, the well to sick progression period for each endpoint will be modelled monotonically. Firstly, a linear mixed effect model for the change from baseline vs. day will be used, with slope (i.e. without intercept) included as both fixed effects and random effects (to account for participant level variation). The number of participants used by the model, estimate of the slope's fixed effect mean, standard error, 90% CI, and p-value, as well as the variance estimate for its random effect will be presented.

Secondly, for the statistically significant endpoints determined by the linear mixed effect model, a logistic sigmoid growth/Emax model will also be considered for the population model:

$$y_{ij} - a_{i0} = \frac{d - a_{i0}}{1 + \left(\frac{\text{day}_j}{c}\right)^{-b}} + \varepsilon_{ij}$$

where i represents the i th participant, j represents the j th day, a_{i0} is the baseline value for the i th participant, and y_{ij} is the continuous endpoint value modelled as response. Parameters b , c , d represent the Hill slope, the day at which 50% effect is reached, and the asymptotic maximum sick response for the model, respectively, which can have participant level variation.

To facilitate model convergence, the maximum value observed during the period for each participant (direction determined by individual linear fit from b above), \max_i , will be used to substitute parameter d , and a linear mixed effect model of the logit transformed $\log((\max_i - y_{ij})/(y_{ij} - a_{i0}))$ vs $\log(\text{day})$ will be used for the longitudinal changes, with its intercept and slope included as both fixed effects and random effects. The number of participants used by the model, estimates of the fixed effect means, standard errors, 90% CIs, and p-values, as well as the variance estimates for their random effects will be presented. The

back-transformed mean estimates and 90% CIs for the parameters b and c , where $b = -\text{slope}$ and $c = \exp(-\text{intercept/slope})$, will also be presented.

Additional models may also be considered as appropriate, and the models' goodness of fit will be assessed using Akaike/Bayesian information criteria.

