5.3. Methods to Manage Missing Data

All summaries and analyses will be based on observed data and missing data imputation is not planned.

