6.1.1. Main Analysis

6.1.1.1. Well to Sick

- Estimator: Primary Estimator E1(Section 2.1.1). This estimator is intended to provide a population level estimate of the well state as well as changes in symptoms and voice features from well to sick in symptomatic SARS-CoV-2, influenza virus, or RSV positive participants using Electronic diary.
- Analysis Sets: (a) Participants in Primary Analysis Set (Section 4) who become SARS-CoV-2, influenza virus or RSV positive (at Swab#2) and symptomatic during the study; (b) A subset of (a) who are symptom free at enrollment; (c) A subset of (a) who have symptoms due to chronic pre-existing conditions at enrollment. These analysis sets will be considered as deemed appropriate by data.
- Intercurrent events and missing data: (a) There are no particular intercurrent events considered. Participants who have events that lead to missing data will be included and missing data will not be imputed. (b) Inadequate compliance – data will be used as recorded.
- Statistical Method: Summary statistics and linear mixed effect analyses as described in Section 5.2.2.3. The total symptom score, each symptom and each voice feature will be modelled individually.
- Summaries:
 - a. Descriptive summaries and corresponding plots of the mean/SD will be provided. For linear mixed effect model analyses, estimates for all parameters fixed effect means, standard errors, 90% CIs, and p-values, as well as the variance estimates for their

random effects will be provided (as described in [Section 5.2.2.3](#)). Results from all models will be presented in a table.

- b. To assess the well-to-sick analysis baseline: For voice features that are determined as statistically significant based on linear model mixed effect analysis, the difference of the voice feature values between every pre-symptomatic day (starting from enrollment day) and the well-to-sick baseline (i.e. 7-day average before symptomatic onset as described in [Section 5.2.2.3](#)) will be computed. The mean/SD of the differences across participants in the analysis set will be plotted by day up to the symptomatic onset.

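### The sigmoid step of the well-to-sick analysis replaces the asymptote with each participant's observed maximum, so its logit is undefined at every peak, no rule covers those rows, and the reported b and c can be distorted.

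*SAP*

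**What the plan says.** SAP 5.2.2.3 models the period from symptom onset to the time before recovery in two steps. A linear mixed model of change from baseline on day comes first. Then, "for the statistically significant endpoints determined by the linear mixed effect model, a logistic sigmoid growth/Emax model will also be considered". In that sigmoid, b is the Hill slope, c the day of half effect, and d is "the asymptotic maximum sick response for the model, respectively, which can have participant level variation".

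To help the fit converge, d is replaced by "the maximum value observed during the period for each participant (direction determined by individual linear fit from b above"). The plan then uses "a linear mixed effect model of the logit transformed" ratio (max_i − y_ij)/(y_ij − a_i0) on log(day), with random intercept and slope. It reports b = −slope and c = exp(−intercept/slope) with 90% CIs, and the number of participants used. SAP Table 1 (version 4) confirms that this is the main form: "the nonlinear sigmoid model was modified to primarily use the logit transformed linear mixed effect model to estimate growth during the period".

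SAP 6.1.1.1 places the output under the primary endpoints: "Results from all models will be presented in a table". The only general rule on unusable data is in SAP 5.3: "All summaries and analyses will be based on observed data and missing data imputation is not planned".

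**The concern.** An asymptote is a level that the curve approaches, while an observed maximum is a data point. Putting the second in place of the first makes the numerator zero on the peak day and on any tied day. The denominator is zero when a value equals baseline, and the ratio is negative when a value lies on the wrong side of baseline for the fitted direction. Such values are to be expected: baseline is an average of earlier days, and symptoms are scored 0–4 or 0–7 (SAP 5.2.3), so ties are common. SAP 5.3 does not help, because these values are observed, not missing.

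Two programmers following the SAP could therefore table different b and c. If the rows are dropped, those that remain are selected on the outcome, and max_i is still not d. A reader would take c as the day of half effect and b as the steepness of onset, with CIs that may exclude both.

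**Working it through.** **1. The back-transformation is correct.** From the SAP's equation, (d − y)/(y − a) = (day/c)^(−b), so the log is b·log(c) − b·log(day). Hence slope = −b and −intercept/slope = log(c). With the true d, b and c are recovered exactly.

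**2. A noise-free example of the substitution.** Assume a = 0, d = 1, b = 2, c = 2.5 and days 1–5. Then y = 0.138, 0.390, 0.590, 0.719, 0.800, so max_i = 0.800.
- (max_i − y)/y = 4.80, 1.05, 0.356, 0.1125, 0. Day 5 is log(0) and is lost.
- Logs for days 1–4: 1.569, 0.049, −1.034, −2.185. Values of log(day): 0, 0.693, 1.099, 1.386.
- Least squares: slope −2.637, intercept 1.694. So b = 2.64 (truth 2) and c = exp(1.694/2.637) = 1.90 (truth 2.5).
- Time to half of the observed peak (y = 0.4): 2.5/√1.5 = 2.04. Much of the shift in c is thus a change of target; the error in b is not.

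**3. Does the handling rule matter?** Assumed grid: six (b, c) pairs from (1.5, 2) to (4, 4), four windows (5, 7, 10, 14 days) and four noise SDs (0.05, 0.10, 0.20, 0.30 of d − a), so 6 × 4 × 4 = 96 scenarios, with pooled fits. Between 7% and 44% of records are undefined.

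| Handling | b off by >10% | c off by >10% |
|---|---|---|
| max_i, drop | 82 (14 up, 68 down) | 56 |
| max_i, clip at 0.01 | 75 | 63 |
| max_i, clip at 0.05 | 76 | 59 |
| true d, drop (control) | 69 (all down) | 0 |

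The control shows that the substitution drives the error in c. Much of the downward error in b comes from logging noisy values and dropping rows, so a boundary rule alone would not cure it. The rule still matters: for b = 2, c = 3, 5 days, SD 0.20, b moves by −14% (drop), +69% (clip 0.01) or +24% (clip 0.05).

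**4. Size with the mixed model.** Assumed: 100 participants, truth b = 2 and c = 2.5, one record per day, undefined rows dropped, noise as a percentage of the plateau. Medians over simulated datasets, with 90% CI coverage where computed:

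| Setting | b | c | Coverage b / c |
|---|---|---|---|
| No participant variation, 3–8 days, no noise | 2.53 | 1.92 | – |
| No variation, 14 days, 5% noise | 1.91 | 2.56 | – |
| No variation, 3–8 days, 50% noise (35% of rows lost) | 0.61 | 3.62 | – |
| Variation*, 3–8 days, 10% noise | 1.98 | 1.99 | 89% / 0% |
| Variation*, 14 days, 10% noise | 1.45 | 2.82 | 0% / 21% |
| Variation*, 14 days, 50% noise | 0.53 | 7.38 | 0% / 0% |
| SAP recovery-rule window, total symptom score | 1.29 | 2.49 | – / 88% |
| SAP recovery-rule window, voice feature, 50% noise | 0.34 | 6.2 | – |

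*Log-SD 0.4 in b and c, 30% in d. The 89% is coverage of the median b; for the mean b of 2.17 it is 31%.

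Rows 2 and 4 show errors cancelling. In the setting of row 4, the average time to half of the observed peak was 1.95, so the fitted c is near that quantity, though far from 2.5.

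**5. The original-scale alternative.** With variation in b, c and d modelled: 1.95/2.53 and 1.98/2.52 at 10% noise (3–8 and 14 days), 2.00/2.45 at 50% noise with 14 days, but 1.89/2.70 at 50% noise with 3–8 days (coverage 76% and 77%).

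Under SAP 5.2.2.2, "the beginning of recovery is defined as the first day after the Maximal Score Day when the total symptom score is decreased", with two further non-increasing days required, so the window can keep post-peak days. There, two simulations for the total score with differing details gave:
- b = 2.19–2.43 and c = 2.16–2.20, against 1.29/2.49 for the logit;
- b = 2.99 and c = 1.67, against 0.59/2.03 for the logit.

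In both, the original-scale fit is nearer the truth on b and further from it on c. In the second simulation it was also worse than the logit for truth b = 1.2, c = 4. For the voice feature it gave 2.34–2.93/1.76–1.78, against 0.34/6.2.

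**The case against.** The SAP openly says that max_i stands in for d, so c can be read as the time to half of the observed peak. With b = 2 and c = 2.5 the curve has reached only 59% of d on day 3 and 91% on day 8, so scoring a short window against the asymptote is harsh. This stands for c in short, low-noise windows. It does not rescue b or the 50%-noise settings, and rescues long windows only in part (in a 14-day setting, fitted c was 2.73 against a half-peak time of 2.43).

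Most of the settings cut the curve at fixed lengths, not by the recovery rule. Under that rule, c for the total score was close to the truth in one simulation. This also stands, although b was low. For the daily total score, day 1 cannot lie at or below baseline, because onset requires a score above the Initial Symptom Score; the baseline problem therefore falls mainly on single symptoms, voice features and later days.

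Convergence is a fair reason for a shortcut: for truth b = 1.2, c = 4 with 50% noise and 3–8 days, only 3 of 7 original-scale fits were usable. The SAP also permits additional models, so a better fit is allowed, but it is not required, and the tabled b and c would come from the logit fit.

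A reader might infer that the well-to-sick analysis as a whole is invalid. The documents do not support that: the by-day summaries, linear mixed slope, Tmax and Growth Rate never use the transform, and SAP 5.1 attaches no decision rule to any result. Nor do they support a fixed direction of bias, or a claim that estimating d removes all bias.

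**Conclusion.** The step is wrong as written: the logit cannot be computed at any participant's peak, and the SAP has no rule for those rows. That much needs no assumptions. Under assumed values, dropping the rows biases b in most settings and c in many, as estimates of the Hill slope and the half-time to the asymptote. In the 96-scenario grid the range was −71% to +56% for b and −30% to +89% for c. Short, quiet windows tend to push b up and c down; long or noisy ones push b down and c up. The sizes depend on b, c, noise and window length, none of which the documents give. Single 0–4 and 0–7 symptoms were not put through the mixed-model simulations, which also used one record per day although SAP 5.2 enters all sessions. The point should be fixed before b and c are tabled, but it touches only those exploratory parameters and their 90% CIs.

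**What to change.** 1. Report b and c from the sigmoid already displayed in SAP 5.2.2.3, fitted on the original scale with d estimated and all observations kept. Use participant-level random effects on b, c and d where the data support them. Otherwise use participant-level bootstrap or cluster-robust CIs and describe b and c as values of the average curve, since such CIs repair width but not shift. With random d only, cluster-robust coverage was still just 40–95% for b and 71–81% for c.
2. Pre-specify the convergence criterion, for example finite standard errors and c inside the observed window. If it fails, report only the by-day change and linear slope, and list the endpoint as having no b and c.
3. State that b and c are conditional on the monotone model, because windows ended by the recovery rule keep post-peak days and bias this fit too. It is not uniformly better than the logit there.
4. If the logit fit is kept, label b and c as descriptive and relative to the observed maximum, state how undefined rows are handled, and report the observations lost as well as the participants used. Its AIC/BIC should not be compared with models of the untransformed response; the SAP does not say that it would be.

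The cost is SAP wording and more programming, and some noisy, short-window endpoints will have no b and c. Item 4 alone is mostly wording, but it leaves the distortion in place.

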5.2.2.4. Well State Analysis

For each of the continuous endpoints during the well state, i.e. from enrollment day to the day before the first occurrence of new or increased symptoms in participants based on Electronic diary, the average of the endpoint values across all days will be summarized for the participants descriptively.

A mixed effects model will also be conducted, with participant and day as random effects, to evaluate the inter-participant variation and intra-participant day by day variation. Gender, age and race may be included as covariates to assess the effects. Estimates of the overall mean value per feature, its standard error, and 90% CI, as well as the variance components will be presented.

5.2.2.5. Correlation Between Symptoms and Voice Features

Change from baseline in symptom, after first occurrence of new or increased symptoms and before return to well state based on Electronic diary, will be modelled using a mixed-effects model with repeated measures (MMRM) with the change from baseline in the voice feature as covariate, day (categorical factor) as fixed effect, and participant as random effect. For the purpose of this analysis, the baseline is defined as the average of the endpoint values during the period up to 7 days before the first occurrence of new or increased symptoms, and the first occurrence of new or increased symptoms at day = 1. The day of return to well state is defined as the first day after the Maximal Score Day (defined in [Section 5.2.2.2](#)) when the total symptom score is less than or equal to the Initial Symptom Score (defined in [Section 5.2.2.1](#)).

Autoregressive AR(1) variance-covariance structure will be used for the MMRM. The estimate of the coefficient for the change in voice feature, its standard error, 90% CI, and p-value will be presented.

Pearson and Spearman rank order correlations between changes in symptoms and voice features will also be computed for each participant across days. These correlations will be summarized across participants. A heatmap plot will also be presented for each of these correlations.

CCI

CCI [REDACTED]

[REDACTED]

[REDACTED]

[REDACTED]

[REDACTED]

[REDACTED]

[REDACTED]

[REDACTED]

[REDACTED]

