9.2. Sample Size Determination

The sample size determination is based on the primary study objective, which is to obtain data to characterize the relationship between symptoms and voice features for acute viral respiratory illness for RT-PCR confirmed SARS-CoV-2, influenza virus, or RSV positive participants as they progress from well to sick states.

For this exploratory study, it is planned to obtain a total of 100 completers who are RT-PCR confirmed negative to SARS-CoV-2, influenza virus and RSV RT-PCR (at swab #1), and SARS-CoV-2, influenza or RSV RT-PCR confirmed positive (at swab #2) reporting new or increased symptoms.

it is estimated that approximately 5500 participants (8700 in total including participants that have been enrolled prior to protocol amendment #1) will be needed to be enrolled in the study.

A reassessment of study feasibility and enrollment requirements is anticipated, including the required sample size, after infection rates and compliance data from the first 1000 completers analyzed.

The case definition that will be used to define cases for the primary objective of the study will be as follows:

Negative RT-PCR at swab #1 and Positive RT-PCR at swab #2 who develop 1 or more new or increased symptoms from baseline from the following list:

Fever, chills, rigors, myalgia, headache, fatigue, sore throat, rhinorrhea, congestion, vomiting, nausea, diarrhea, new olfactory and taste disorder(s), cough, wheezing, shortness of breath, or difficulty breathing.

Depending on the distribution of the 3 viruses, this sample size may be adequate to build general algorithm(s) for early detection of upper respiratory illnesses. This sample size will allow identification of any additional data required to finalize this algorithm(s).

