5.2. General Methods

Data will be summarized using descriptive statistics (number of participants (n), mean, median, standard deviation (SD), minimum and maximum, as appropriate) for continuous (or near continuous) variables, and using frequency and percentages for discrete variables.

Participants can complete the Electronic diary multiple times per day, and each time is considered a session. The session with the most compliant voice and symptom data, and the highest quality voice data will be used for that day to compute the summary statistics. All individual sessions will be used for statistical modeling.

P-values will be generated where appropriate and any p-value < 0.10 will be considered statistically significant. Due to the exploratory nature of the study, p-values will not be adjusted for multiplicity. P-values will be rounded to 3 decimal places and therefore presented as 0.xxx; P-values smaller than 0.001 will be reported as '<0.001'.

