6.1.1.3. Correlation of Symptoms and Voice Features

- Estimand: Primary Estimand E1([Section 2.1.1](#)).
- Analysis Sets: (a) Participants in Primary Analysis Set ([Section 4](#)) who become SARS-CoV-2, influenza virus, or RSV positive (at Swab#2) and symptomatic during the study; (b) A subset of (a) who are symptom free at enrollment; (c) A subset of (a) who have symptoms due to chronic conditions at enrollment. These analysis sets will be considered as deemed appropriate by data.
- Intercurrent events and missing data: (a) There are no particular intercurrent events considered. Participants who have events that lead to missing data will be included and missing data will not be imputed. (b) Inadequate compliance – data will be used as recorded.

- Statistical Method: MMRM model, and Pearson and Spearman rank order correlations, as described in [Section 5.2.2.5](#).
- Summaries: Estimates of the coefficient for the change in voice features, standard errors, 90% CIs, and p-values will be summarized. Results from all models and the correlations will be presented in a table. Correlation plots will be presented.

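### The symptom-voice model in SAP 5.2.2.5 reports one coefficient that blends person-level well-to-sick shifts with day-to-day tracking, so it can be read as neither

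*SAP*

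**What the plan says.** The model is in SAP 5.2.2.5. The outcome is "Change from baseline in symptom, after first occurrence of new or increased symptoms and before return to well state based on Electronic diary". It is modelled "with the change from baseline in the voice feature as covariate, day (categorical factor) as fixed effect, and participant as random effect", and "Autoregressive AR(1) variance-covariance structure will be used for the MMRM". One result per voice feature is reported: "The estimate of the coefficient for the change in voice feature, its standard error, 90% CI, and p-value will be presented". SAP 6.1.1.3 makes this a main analysis under the primary estimand: "Estimates of the coefficient for the change in voice features, standard errors, 90% CIs, and p-values will be summarized".

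Three other places bear on the reading.

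- SAP 5.2 sets the threshold, "any p-value < 0.10 will be considered statistically significant", without multiplicity adjustment.
- SAP 5.2.2.5 adds a second method: "Pearson and Spearman rank order correlations between changes in symptoms and voice features will also be computed for each participant across days". These correlations are summarized across participants and shown in a heatmap. No confidence interval or test is stated for them.
- SAP 6.1.2 plans a sensitivity analysis for diary compliance only.

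No section centres voice change on the participant's own mean or adds that mean as a separate term.

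**The concern.** Voice change varies in two ways. Participants differ in how far their voice moves on average between the well and sick states, and each participant's voice also moves from one illness day to the next. A random participant intercept with a single slope estimates neither association alone. It averages them, with weights set by the variance components and by how many days each illness lasts.

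The two associations answer different questions. The first asks whether people with a larger voice shift also have a larger symptom shift. The second asks whether voice follows symptoms over the course of one illness. The protocol wants these data to support algorithms that both detect and monitor illness, so each question matters. With one blended coefficient, a small p-value does not say which association produced it. Two voice features could also be ranked differently only because their variance splits between people and days differ.

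**Working it through.** The documents give no power or error rate for this model, so there is no stated figure to reproduce. The check is the algebra of the estimator, followed by simulation.

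**Inputs from the documents.** There are 100 cases (Protocol 9.2: "it is planned to obtain a total of 100 completers who are RT-PCR confirmed negative"). The threshold is p<0.10, taken as two-sided because it is paired with 90% CIs. The model is that of SAP 5.2.2.5.

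**Assumptions not in the documents.** One observation per day, balanced windows of 5 to 14 days, and total variance 1 for each variable. The between-person share of variance is 0.3 to 0.7. The daily AR(1) is 0.5 for symptoms and 0.3 for voice. The person-level correlation r_b is 0 to 0.7. Day-to-day tracking is set to zero.

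**Algebra.** Leaving AR(1) aside for transparency, with m days per person:

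- slope = (λB·b_between + W·b_within) / (λB + W), where λ = σe² / (σe² + mσu²)
- B and W are the between- and within-person sums of squares of voice change. Per person, B is about m·s_b + s_w and W is (m−1)·s_w, where s_b and s_w are the between- and within-person variances of voice change.

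With equal shares (0.5 and 0.5):

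- 10 days: λ = 0.5/5.5 = 0.091, B = 5.5, W = 4.5. Between-person weight = 0.5/(0.5 + 4.5) = 10%.
- 5 days: λ = 0.5/3 = 0.167, B = 3, W = 2. Between-person weight = 0.5/2.5 = 20%.

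The weight therefore depends on illness length.

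**Simulation.** REML fit with random intercept, AR(1) and day as a factor, 600 replicates per row. The Monte Carlo standard error is about 1 to 2 points; for example √(0.3 × 0.7/600) = 1.9 points. There are 100 participants except in the last row. Because the true within-person slope is zero, the between-person weight is the SAP coefficient divided by the person-level coefficient.

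| Days | r_b | Between-person share, symptom/voice | Mean SAP coefficient | SAP coefficient p<0.10 | Person-level coefficient after split | Weight | Deviation term p<0.10 |
|---|---|---|---|---|---|---|---|
| 10 | 0 | 0.5/0.5 | −0.001 | 11.5% | −0.004 | n/a | 11.2% |
| 10 | 0.3 | 0.5/0.5 | 0.019 | 15.8% | 0.253 | 7.5% | 9.5% |
| 10 | 0.5 | 0.5/0.5 | 0.032 | 29.8% | 0.428 | 7.5% | 6.8% |
| 10 | 0.7 | 0.5/0.5 | 0.045 | 49.3% | 0.596 | 7.6% | 9.5% |
| 5 | 0.3 | 0.5/0.5 | 0.034 | 23.8% | 0.229 | 15% | 11.8% |
| 5 | 0.5 | 0.5/0.5 | 0.062 | 42.8% | 0.382 | 16% | 10.5% |
| 14 | 0.5 | 0.5/0.5 | 0.025 | 31.7% | 0.443 | 5.6% | 10.5% |
| 10 | 0.5 | 0.3/0.3 | 0.024 | 21.8% | 0.353 | 6.8% | 9.3% |
| 10 | 0.5 | 0.3/0.7 | 0.077 | 62.2% | 0.307 | 25% | 11.3% |
| 5 | 0.5 | 0.3/0.7 | 0.107 | 66.2% | 0.286 | 37% | 11.7% |
| 7 (50 participants) | 0.5 | 0.5/0.5 | 0.042 | 23.2% | 0.402 | 10% | 11.5% |

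A separate simulation with r_b of 0.3 to 0.5 and windows of 4 to 14 days gave 16% to 61% for the SAP coefficient and 7% to 15% for the deviation term.

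The blend also loses information in the other direction. With 10 days and r_b = 0.3, the person-level term after the split is significant in 79.8% of replicates, against 15.8% for the SAP coefficient. In a 4-day case the SAP coefficient is about 0.07 where the person-level coefficient is 0.36.

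The mean per-participant Pearson correlation is 0.00 in every row (−0.003 to 0.006).

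**The case against.** The strongest reply concerns what the person mean represents. The covariate is not raw voice but change from the participant's own pre-onset baseline, so stable voice differences between people are largely removed already. What remains at person level is the average move from well to sick, and that change is the primary endpoint (SAP 3.1). When 7 well days are added to 7 sick days in data of the same kind (r_b = 0.5, no day-to-day link in the sick window), the purely person-centred slope is 0.05 to 0.20. It is significant in 52% to 99% of 600 replicates, against 10% to 12% when r_b is zero. This stands. A reader might infer that a significant coefficient is spurious, or that only the deviation term measures the symptom-voice relationship. The documents support neither. Centring on the sick-window mean removes the well-to-sick shift, and the appendix algorithm is a screening tool that separates well from sick states.

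Other points stand in part.

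- The per-participant correlations are a within-person analysis, and in these scenarios they would sit near zero and show the discrepancy. But they carry no stated interval or test, and the SAP does not say how to read a conflict with the model.
- The rates depend on assumed correlations, variance shares and windows. Very short windows may not be typical, because the window closes only when the total score, after its maximum, falls to the Initial Symptom Score or below.
- The study is exploratory and SAP 5.1 sets no decision rules. That limits the consequence, but it does not settle what the coefficient estimates.

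**Conclusion.** The point holds as one of interpretation: the single coefficient can be read neither as the person-level association of well-to-sick shifts nor as day-to-day tracking. The random intercept puts most of the weight on the within-person slope (63% to 94% in the table). The contamination is therefore modest in absolute size, with a mean coefficient of 0.02 to 0.11 at r_b of 0.3 to 0.5. It still matters for the p-value, which falls below 0.10 in roughly 16% to 61% of simulated studies without tracking, and in 66% in the most extreme row. All of this rests on a non-zero person-level correlation. At r_b = 0 the rate is 11.5%, which is no material excess over the nominal 10%. The conclusion that two associations are mixed needs none of these assumptions; only its size does.

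**What to change.** In SAP 5.2.2.5, replace the single voice covariate by two terms: the participant's mean voice change over the analysis window, and each day's deviation from that mean. Here and in 6.1.1.3, report both coefficients with standard error, 90% CI and p-value. Label the mean term as the person-level association of well-to-sick shifts and the deviation term as day-to-day tracking during illness. Name neither as the sole symptom-voice relationship. The cost is SAP wording, one more covariate and one more reported column per model. No new data are needed.
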